#### **8.2.3.1. CDSD v2.1**

The CDSD v2.1, a novel patient-reported outcome measure developed for use with participants with CeD, consists of five symptoms including diarrhea, abdominal pain, bloating, nausea, and tiredness. The CDSD v2.1 assesses severity, in five scales from “none” to “very severe”, and frequency. The CDSD v2.1 will be assessed daily as part of the eDiary beginning during the screening period after signing the ICD.

The CDSD v2.1 should be completed for at least 7 consecutive days during screening at any time prior to the baseline visit (Day 1). After screening and through the end of the study, compliance with the CDSD v2.1 is defined as 80% completion.

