1.3. Sample Size

A sufficient number of participants will be screened to achieve approximately 52 treated participants (26 per study arm). The sample size calculation is based on the primary efficacy estimand and its endpoint, changes from baseline in the ratio of Vh:Cd at Day 29 visit. With

an overall 2-sided type I error rate of 5%, the study will have approximately 94% power under a sample size of 26 participants per arm to detect a treatment difference in LSM of 0.50 in change in ratio of Vh:Cd between treatment arms, assuming that the common standard deviation is 0.5 and the difference between the means is 0.5. To adjust for multiple looks, the O'Brien-Fleming adjustment is applied to control overall type I error rate to ensure that the overall Type I error rate remains at 5%. The interim analysis will be evaluated at significance level 0.003 and the final look will be evaluated at significance level 0.049.

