2.3. Exploratory Endpoints

- Changes from baseline in Marsh-Oberhuber score assessed via EGD with biopsy after 2-week GC.
- The biopsy will be performed at screening and Day 29, or ET visit. Baseline is the last non-missing Marsh-Oberhuber score at screening.
- CSDS

- CDSD is a patient reported outcome (PRO) questionnaire collected daily. The version 2.1 includes 5 severity items and 3 frequency supplement questions (see [Appendix 2.2](#)) that will be collected daily.
 - CDSD Total Score is the sum of all 5 severity items. The CDSD Weekly Average Total Score will be calculated , for details on the calculation see below, Section [5.3.2](#) and [Appendix 2.2](#).
 - The CDSD Gastrointestinal (GI) Domain Score is the sum of items 1-4. The CDSD Weekly Average Gastrointestinal (GI) Domain Score will be calculated, for details on the calculation see below, Section [5.3.2](#) and [Appendix 2.2](#) .
 - For CDSD Nausea score and vomiting frequency, in addition to weekly average score, 3-day average will be derived as well (every 3 days start from Day 15 GC until Day 41). If 2 observations are missing, the 3-day average score will not be calculated. Day 15 Nausea score and vomiting frequency will be analyzed as well.
- For CDSD Total score, GI Domain score, individual severity item and frequency supplement question, the Baseline value is the average of most recent 7-day interval scores before Day 1 (not include Day 1) with at least 4 days with non-missing scores, and will be used as the baseline to calculate the change from baseline to the 1-day, 3-day average and weekly average. If there are ≥ 4 days missing scores in any 7-day interval before Day 1, the baseline value is set as missing.
- For post-baseline weekly average score calculation, Week 1 is from Day 1 to Day 7, Week 2 is from Day 8 to the day before Day 15 GC, Week 3 is from the day after Day 15 GC to Day 21. The number of days for Week 2 and Week 3 maybe equal to, less than, or greater than 7. See Section [5.3.2](#) for the details. The weekly average score is the weekly sum score divided by the number of days with non-missing in that week. If daily scores are missing for more than half of total days in a specific week, the average score is missing for that week.
- Change from baseline at each timepoint = observed (or derived as described above) value at each timepoint – baseline.
- The observed value and the change in PGIS

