5.3.2. CDSD

The weekly average score of each severity item and frequency question of CDSD (Diarrhea, Abdominal Pain, Bloating, Nausea, Number of times Vomiting, Tiredness, Number of Bowel Movements and Number of events of Diarrhea) as well as the weekly average CDSD Total Score, weekly average CDSD GI Domain Score (see [Section 2.3](#) and [Appendix 2.2](#)) and change from baseline will be descriptively summarized as stated in Section 5 for each treatment group by timepoint.

The change from baseline for weekly average of each of the 5 severity items and 3 frequency questions, the weekly average CDSD Total Score, and the weekly average CDSD GI Domain Score will be analyzed using ANCOVA models in [Section 4.2.1](#) by timepoint. LSM of the treatments with 95% CI, LSM of the treatment difference with PBO, p-value and 95% CI will be generated.

If there are multiple records on a same day, the earliest one will be used for analysis.

The analysis set(s) used for these endpoints are found in Section [5](#).

Weekly Time Definitions:

	Regardless the day of Day 15 GC	Day 15 GC is at day 14	Day 15 GC is at day 15	Day 15 GC is at day 16	Day 15 GC is at day 17
Baseline	Day -7 to -1				
Week 1	Day 1 to 7				
Week 2		Day 8 to 13	Day 8 to 14	Day 8 to 15	Day 8 to 16
Week 3		Day 14 to 21	Day 15 to 21	Day 16 to 21	Day 17 to 21
Week 4	Day 22 to 28				
Week 5	Day 29 to 35				
Week 6	Day 36 to 42				

In addition, the change from baseline in CDSD Nausea score and vomiting frequency for Day 15, 3-day average and 7-day average (weekly average) score, will be summarized as stated above, and analyzed within placebo and KAN treatment, evaluating the paired difference from baseline using the Wilcoxon Signed-rank test. The Mann-Whitney U test (Wilcoxon Rank Sum test) will be used to test the difference in the change from baseline for placebo vs KAN-101. The median difference between treatment groups estimated by the Hodges–Lehmann method along with the 95% CI will be reported as well.

Line plots by treatment group will be provided for LSM 95% CI).

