Appendix 1. Summary of Efficacy/Exploratory Analyses

Endpoint	Analysis Type	Population	Analysis Model
Change from baseline in Vh:Cd ratio at Day 29	Summary	FAS	N/A
	Main analysis	FAS	ANCOVA with terms treatment, baseline
	Sensitivity/supplementary analysis	PPS, SAS	ANCOVA with terms treatment, baseline
GC IL-2 (log-transformed) change from Day 15 pre-GC to Day 15 post GC	Summary	BAS	N/A
	Analysis	BAS	ANCOVA with terms treatment, baseline
	Sensitivity/supplementary analysis	PPS, SAS	ANCOVA with terms treatment, baseline
Changes from baseline in IEL density in duodenum biopsy after 2-week GC (at Day 29)	Summary	FAS	N/A
	Analysis	FAS	ANCOVA with terms treatment, baseline
	Sensitivity/supplementary analysis	PPS, SAS	ANCOVA with terms treatment, baseline

Endpoint	Analysis Type	Population	Analysis Model
CDSD change from baseline at each timepoint	Summary	FAS	N/A
	Analysis	FAS	ANCOVA with terms treatment, baseline
	Sensitivity/supplementary analysis	PPS, SAS	ANCOVA with terms treatment, baseline
CDSD 1-Day, 3-Day, 7-Day Nausea Score and Vomiting Frequency and change from baseline at each timepoint post-gluten challenge	Summary	FAS	Observed cases
	Analysis	FAS	All data collected will be included regardless of intercurrent events. Missing data will not be imputed. Wilcoxon Signed-rank test for change from baseline within each group
	Analysis	FAS	All data collected will be included regardless of intercurrent events. Missing data will not be imputed. Mann-Whitney U test (Wilcoxon)

Endpoint	Analysis Type	Population	Analysis Model
			Rank Sum test) for comparison of placebo vs KAN group for change from baseline
PGIS change from baseline at each timepoint	Summary	FAS	N/A
	Analysis	FAS	ANCOVA with terms treatment, baseline
PGIC at each timepoint	Summary	FAS	N/A
	Analysis	FAS	ANOVA with term treatment
Marsh- Oberhuber score	Summary	FAS, PPS, SAS	N/A

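### The within-arm signed-rank test on Day 15 nausea compares one day with a 7-day mean and so leans toward improvement when nausea is sporadic

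*SAP*

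**What the plan says.** For the CDSD items, SAP 2.3 states that "the Baseline value is the average of most recent 7-day interval scores before Day 1", provided at least four of those days have a score. That one value "will be used as the baseline to calculate the change from baseline to the 1-day, 3-day average and weekly average". SAP 2.3 also says that "Day 15 Nausea score and vomiting frequency will be analyzed as well", so a single-day value is compared with a 7-day mean.

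Under SAP 5.3.2 the change will be "analyzed within placebo and KAN treatment, evaluating the paired difference from baseline using the Wilcoxon Signed-rank test", and Appendix 1 repeats this as "Wilcoxon Signed-rank test for change from baseline within each group". For the randomised comparison, 5.3.2 says: "The Mann-Whitney U test (Wilcoxon Rank Sum test) will be used to test the difference in the change from baseline for placebo vs KAN-101". It adds a Hodges–Lehmann median difference with a 95% confidence interval.

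The SAP gives no significance level for these tests and does not say how zero differences are handled. Protocol 9.2.2 makes no adjustment for multiple endpoints. The analysis is exploratory, and Protocol 9.4.4 allows such results to stay internal and out of the study report.

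**The concern.** When nothing has changed, the signed-rank test holds its error rate only if the paired differences are symmetric about zero. A person with occasional nausea scores 0 on most single days, yet has a small positive 7-day mean. The usual difference is therefore small and negative, with a rare large positive one. The mean difference is zero but the distribution is not symmetric.

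Day 15 is the first day of the gluten challenge. A significant within-arm improvement on that day would invite a favourable reading of whichever arm showed it, when the form of the contrast alone can produce it. The sponsor added this nausea and vomiting analysis on purpose in SAP version 4, so the p-values will probably be looked at.

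**Working it through.** **The plan's own figure.** The documents state no error rate or power for the nausea tests. Their power figure of about 94% (SAP 1.3: 26 per arm, difference 0.5, SD 0.5) concerns Vh:Cd. It reproduces at 94.2% by noncentral t at two-sided 0.05 (94.1% at 0.049) and does not bear on this point.

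**Inputs from the documents.** 26 per arm (SAP 1.3); baseline, Day 15 value and tests as set out above; five severity levels (Protocol 8.2.3.1); the dropout example in Protocol 9.6, which leaves 26 × 0.8 ≈ 21 and 26 × 0.6 ≈ 16 evaluable.

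**Inputs assumed.** Scores coded 0–4; two-sided 5%, hence 2.5% in each direction; share of days with nausea; within-person correlation; zero differences dropped unless stated.

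**Step 1: why the test is off-centre.** Let D = Day 15 score minus the mean of 7 earlier days. In the simplest case, every participant has nausea on 20% of days, independently, scored 0 or 1.

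- Mean of D = 0.20 − 0.20 = 0.
- P(D < 0) = 0.8 × (1 − 0.8⁷) = 0.8 × 0.790 = 0.632.
- P(D > 0) = 0.2 × (1 − 0.2⁷) = 0.200.
- Share of non-zero differences that are negative = 0.632 / 0.832 = 0.760.

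The signed-rank statistic in effect counts pairs of participants whose two differences sum to more than zero. Under symmetry, half of pairs do. Here a positive sum needs at least one positive member, so the share is at most 1 − 0.760² = 0.42. The statistic is centred below its null value although the mean change is zero.

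If days are exchangeable, one day minus one day has the same distribution as its negative and is symmetric. The same holds for two 7-day means. It does not hold for one day against seven.

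**Step 2: size, simulated with no change.** Latent-normal daily scores, 26 per arm, probability of a significant improvement (nominal 2.5%):

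| Days with nausea | Within-person correlation 0–0.4 |
|---|---|
| 5% | 13–29% |
| 10% | 15–31% |
| 20% | 12–22% |
| 30% | 9–14% |
| 40% | 7–9% |
| 60% | 4–6% |

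At correlation 0.6 the rate is 4–10%, and at 0.8 it is 1.5–6%, over 5–60% of days. False worsening is at most 1% when nausea is on 30% of days or fewer.

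A second model draws each person's daily probability from a beta distribution. Over 5–30% of days it gives two-sided rejection of 15–32% with no between-person variation, 13–19% with moderate and 8–13% with strong variation. At least about 95% of these rejections point to improvement. Together the two models give roughly 8–32%.

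**Step 3: where it shrinks or grows.**

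- Fewer evaluable: 0.3–23% at 16 and 0.5–28% at 21, over all latent-normal settings.
- Half of participants never nauseated, 26 per arm: about 2–25% in one set of runs, and 1–10% in another with strong variation among the rest. With 70% never nauseated: 0.6–6%.
- Strong variation, tie-exact test, nausea on 5% of days: 3.7% at 26 and 0.6% at 16.
- Zeros kept in the ranking (Pratt), 10–30% of days, correlation 0.2–0.6: 11–42%.

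**Step 4: other contrasts, 26 per arm, no change.** False improvement is at most about 2.8% for one day against one day, 1.6–3.3% for 7 days against 7, and 2.4–4.5% for the planned 3-day against 7-day mean. The fault is confined to the 1-day contrast.

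**Step 5: between arms, 26 per arm.** Rank-sum type I error is 3.7–6.2%. Power depends on how Day 15 nausea relates to baseline. Two examples with baseline nausea on 20% of days and within-person correlation 0.4:

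| Relation of Day 15 to baseline | Day 15 nausea, placebo vs KAN-101 | Power, planned change | Power, Day 15 score alone |
|---|---|---|---|
| Unrelated | 40% vs 10% | 49% | 77% |
| Correlation 0.6 | 60% vs 25% | 81% | 77% |

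At correlation 0.6 the results run from a 25-point loss to a 7-point gain. If Day 15 is the same trait plus a shift, the planned change is within 2 points of the raw score or better, by up to 17 points.

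**The case against.** The strongest reply is that false improvement requires an arm with no change on the first day of a gluten challenge. In one simulation (baseline nausea on 10% of days, strong between-person variation), raising Day 15 nausea to at least 40% gave detected worsening in 74% of arms at 26 and 44% at 16, with no false improvement. With Day 15 nausea at 20%, false improvement was 0.2–0.5%. This stands: the problem lies with arms that react little or not at all.

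The bias also acts in both arms, and the same paragraph of the SAP supplies a randomised comparison. A reader might infer that the plan would wrongly show protection by KAN-101. The documents do not support that, because a within-arm p-value is not the treatment comparison and the decision rule in SAP 4.1 concerns only Vh:Cd.

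A reader might also infer that the rank-sum test loses power. That is not general: the loss can vanish or reverse (Step 5). Masking of real worsening is conditional too. When Day 15 nausea rose by 20 points, detection fell by 7–12 points against a one-day comparator at correlation 0.2 with nausea on 10–20% of days, and did not fall at correlation 0.6.

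None of this removes the asymmetry. The within-arm test still has the wrong reference distribution in the no-change case it is meant to guard against.

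**Conclusion.** The point holds for one analysis. The within-arm signed-rank test on the 1-day Day 15 nausea change is biased toward improvement when nausea is sporadic. Under the stated assumptions (26 per arm, nausea on 5–30% of days, low to moderate within-person correlation) the false-improvement rate is roughly 8–32% rather than 2.5%. Strong within-person correlation, many never-nauseated participants or fewer evaluable participants can reduce it to about 0–10%, though none of these guarantees it (Step 3).

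It would be tempting to say flatly that 10–30% of unchanged arms will show a false improvement. The documents give neither the daily nausea rate nor the correlation, so only a conditional range can be stated. Sporadic nausea is plausible after at least 12 months on a gluten-free diet (Protocol 5.1), and blinded screening diaries could check it.

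Nor do the results support changing the 7-day baseline elsewhere: the 3-day and weekly contrasts are close to nominal. The between-arm test keeps its type I error, and the primary analysis is untouched. Severity is minor.

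**What to change.** For the 1-day Day 15 nausea analysis only, amend SAP 2.3, 5.3.2 and Appendix 1 in one of two ways:

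- drop the within-arm signed-rank p-value and report the change descriptively; or
- compare Day 15 with one prespecified single diary day before the challenge. The SAP should say whether that day falls before or after dosing, since the question differs.

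In either case, base inference on the between-arm comparison. A rank ANCOVA of the Day 15 score adjusting for ranked baseline is an option. Leave the 3-day and weekly analyses as they are.

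The cost is SAP wording and minor programming, with no new data because the diary is already daily. The first option gives up one exploratory within-arm p-value. The second accepts a noisier comparator.

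### For vomiting frequency on Day 15 and in the 3-day windows, the only planned between-arm estimate with a CI is a Hodges-Lehmann median difference, which will usually be exactly 0 if fewer than about half of placebo participants vomit

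*SAP*

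**What the plan says.** SAP 2.3 sets up the short windows: "For CDSD Nausea score and vomiting frequency, in addition to weekly average score, 3-day average will be derived as well". The 3-day averages start at the Day 15 gluten challenge and run to Day 41, and Day 15 is also analysed alone. Baseline is a 7-day pre-dose average.

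SAP 5.3.2 then plans two layers of analysis.

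- **Weekly averages.** "The change from baseline for weekly average of each of the 5 severity items and 3 frequency questions" goes into an ANCOVA. The listed items include "Number of times Vomiting, Tiredness, Number of Bowel Movements and Number of events of Diarrhea", so vomiting is covered. The output is specified: "LSM of the treatment difference with PBO, p-value and 95% CI will be generated".
- **Nausea and vomiting only.** A further paragraph covers "the change from baseline in CDSD Nausea score and vomiting frequency for Day 15, 3-day average and 7-day average (weekly average) score". Within each arm the plan is "evaluating the paired difference from baseline using the Wilcoxon Signed-rank test". Between arms, a Mann-Whitney test "will be used to test the difference in the change from baseline for placebo vs KAN-101". The effect estimate beside that test is "The median difference between treatment groups estimated by the" Hodges-Lehmann method, with a 95% CI.

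SAP 5 adds by-arm descriptive statistics (n, mean, SD, quartiles, range), and 5.3.2 applies these to the Day 15, 3-day and weekly values. SAP Appendix 1 gives the 1-day, 3-day and 7-day nausea and vomiting analyses their own rows, and those rows name only the rank tests.

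**The concern.** The Hodges-Lehmann estimate is the median of all between-arm pairwise differences. It suits a score spread over several values. Vomiting frequency in a short window may instead be zero for many participants and a small count for the rest. When many pairs are zero minus zero, the median pair sits on that tie and the estimate is exactly 0, whatever the difference in vomiting rates.

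The rank-sum test does not share this weakness, because it responds to an excess of vomiters in one arm. A table could therefore show a difference of 0, even with a CI of 0 to 0, beside a p-value near 0.01. At stake is whether the output for the acute post-gluten windows, which SAP version 4 added specifically, can be interpreted.

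**Working it through.** **The plan's own figure.** There is none for this endpoint. The documents give no rate, sample size or power for vomiting, so every rate below is an assumption.

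**Inputs.** Planned size is 26 per arm (SAP 1.3). A smaller case uses the dropout example in protocol 9.6: 26 × 0.80 = 20.8, about 21 on KAN-101, and 26 × 0.60 = 15.6, about 16 on placebo. Baseline vomiting is taken as 0 unless stated.

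**When the estimate leaves 0.** One arm must exceed the other in more than half of all pairs. Let p₁ be the placebo proportion vomiting and p₀ the KAN-101 proportion. With similar, untied counts among vomiters:

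P(placebo > KAN-101) = p₁(1 − p₀) + ½p₁p₀

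Setting this to 0.5 gives p₁ = 0.5 / (1 − p₀/2). The placebo rate needed is 50% at p₀ = 0%, 53% at 10%, 56% at 20% and 59% at 30%.

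**Two worked data sets**, 26 per arm, so 26 × 26 = 676 pairs. Vomiters have 1, 2 or 3 episodes in rotation, and differences are placebo minus KAN-101. The median lies between the 338th and 339th ordered differences. The CI limits are the 230th and 447th, from 338 − 1.96 × √(676 × 53/12) = 230.9, rounded down.

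- *8 versus 1 vomiters.* There are 18 negative, 453 zero and 205 positive pairs. Zeros fill ranks 19 to 471, so the estimate is 0 and the CI is 0 to 0. The rank-sum p is 0.010. The mean difference is (15 − 1)/26 = 0.54 episodes and the difference in proportions is 7/26 = 27 points.
- *13 versus 4 vomiters.* There are 66 negative, 304 zero and 306 positive pairs. Zeros fill ranks 67 to 370, so the estimate is 0 and the CI is 0 to 1. The rank-sum p is 0.009. The mean difference is (25 − 7)/26 = 0.69 episodes and the difference in proportions is 9/26 = 35 points.

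**Simulation of single-day counts**, 1 + Poisson(1) episodes among vomiters, 1,500 trials per row, 26 per arm:

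| Placebo vs KAN-101 vomiting | Estimate = 0 | Estimate = 0 among trials with p < 0.05 |
|---|---|---|
| 30% vs 5% | 99% | 98% |
| 40% vs 10% | 92% | 89% |
| 50% vs 10% | 63% | 59% |
| 60% vs 20% | 42% | 31% |
| 70% vs 30% | 23% | 5% |
| 80% vs 40% | 15% | under 1% |

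Repeat runs gave 91% to 92% in the second row and about 40% in the fourth. With 21 and 16 participants, 40% versus 10% gave about 86% overall and about 76% among significant trials.

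**Sensitivity.** Weekly counts behave alike: at 40% versus 10% the figures are 90% and 86%. Letting 5% of participants vomit at baseline lowers those to 87% and 81%. The 3-day windows were not simulated separately; they lie between the one-day and weekly cases.

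**The case against.** The strongest objection is that the SAP reports the size of the effect in other ways. The Hodges-Lehmann paragraph is an addition to the weekly ANCOVA, which already gives a least-squares mean difference with a 95% CI for number of times vomiting. Means by arm are planned for every window. Protocol 8.2.1 has symptoms of the challenge recorded as adverse events, and SAP 5.5.1 counts participants by preferred term and summarises challenge-related events separately. This stands, and it removes any claim that the plan never shows the size of the effect. It does not supply a between-arm estimate with a CI for Day 15 or a 3-day window. Appendix 1 lists ANCOVA for CDSD change at each timepoint, but the text of 5.3.2 confines that model to weekly averages and the appendix gives the short windows separate rows.

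Second, the low vomiting rate is assumed. Protocol Appendix 10 introduces a table that includes vomiting as GI disorders seen frequently in the first-in-human study. No proportion is given, so this neither confirms nor excludes a rate below one half in a short window. There is reason to expect low rates in some windows. If the challenge starts on Day 15, the windows for Days 30–32, 33–35, 36–38 and 39–41 fall wholly after gluten stops on Day 28. Still, a reader might infer that the estimate is zero for almost any plausible result, and the table shows that this fails from about 60% placebo vomiting upward.

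Third, a reader might infer that the within-arm signed-rank test should go, because with 5 non-zero changes its smallest exact two-sided p is 2/2⁵ = 0.0625. A non-significant result is reasonable when so few participants change, so dropping the test is a preference only.

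Fourth, the endpoint is exploratory, and protocol 9.4.4 says such results may not appear in the study report. That limits the importance of the point.

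**Conclusion.** The concern holds in a limited form. For change in vomiting frequency on Day 15 and in each 3-day window, the single planned between-arm estimate with a CI will usually be exactly 0 if fewer than about half of placebo participants vomit in that window, and it can stand beside a significant rank-sum test. At assumed rates of 10% versus 40% this happens in roughly 86% to 92% of trials, depending on arm size. At 20% versus 60% it is about 40%.

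The conclusion rests on an assumed vomiting rate, little vomiting at baseline and similar counts among vomiters in the two arms. The documents do not support extending it to weekly vomiting frequency, where ANCOVA supplies an estimate, or to the nausea score, which was not examined here. The primary analysis and sample size are unaffected. This is a minor, optional improvement.

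**What to change.** In SAP 5.3.2 and Appendix 1, for vomiting frequency on Day 15 and in each 3-day window:

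- add the number and percent of participants with any vomiting by arm;
- add the risk difference with a 95% CI (Miettinen-Nurminen or Newcombe);
- keep the rank-sum p-value and the planned by-arm means;
- keep Hodges-Lehmann as the main effect estimate for the nausea score only.

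The existing rule for missing days in a 3-day average can define who is evaluable. The weekly ANCOVA and the signed-rank test can stay as planned.

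The cost is SAP wording and one exploratory table from diary data already collected. With Day 15 and nine 3-day windows (27 days from Day 15 to Day 41, divided by 3), the table has ten comparisons and should be labelled descriptive. The downside is that any vomiting ignores the number of episodes; the planned means cover that.
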